NSAIDs	Nonsteroidal Anti-inflammatory Drugs
USTY	University of Science and Technology, Yemen
VAS	Visual Analogue Scale

Chapter 1:

Introduction

1.1. Background

The surgical removal of impacted third molars, commonly known as wisdom teeth, remains a frequent procedure in oral and maxillofacial surgery. While the procedure itself is routine, it often leads to undesirable post-operative complications such as pain, trismus (limited jaw opening), and facial swelling (Al-Khateeb & Nusair, 2008; Brković et al., 2017). These complications arise from the natural inflammatory response triggered by the surgical trauma.

Traditionally, the management of these complications has relied on pharmacological interventions, primarily corticosteroids and nonsteroidal anti-inflammatory drugs (NSAIDs) (Kaplan & Eroğlu, 2016). These medications offer potent anti-inflammatory and analgesic properties, effectively reducing pain and swelling. However, their use is often associated with undesirable side effects, including gastrointestinal bleeding, renal dysfunction, and blood dyscrasias, raising concerns regarding their long-term safety (Piecuch, 2012). Recognizing these limitations, researchers have explored alternative therapies with potentially fewer side effects. Among these promising alternatives are therapeutic enzymes and phytotherapeutic drugs derived from natural sources.

Serratiopeptidase, a proteolytic enzyme, has emerged as a potential candidate for managing post-surgical inflammation. Studies have shown its effectiveness in reducing inflammation around teeth and dental implants, suggesting its potential benefit after third molar extraction (Sannino et al., 2013; Villafuerte-Nuñez et al., 2013). However, existing research in this area remains limited, particularly regarding its efficacy in managing post-operative complications following third molar teeth removal.

Similarly, phytotherapeutic drugs offer a promising avenue for post-surgical pain and swelling management. These natural extracts have demonstrated their effectiveness

in treating various inflammatory conditions and postsurgical complications (Olmedo-Gaya et al., 2016; Pavan et al., 2012). Notably, studies have shown their ability to reduce pain and discomfort after third molar surgery, highlighting their potential as safe and effective therapeutic options (Isola et al., 2019). One such phytotherapeutic drug, escin, derived from horse chestnut, has exhibited potent anti-inflammatory activity, suggesting its potential benefit in reducing post-surgical inflammation and swelling (Wang et al., 2009).

Despite the promising results observed with both serratiopeptidase and escin, significant research gaps remain regarding their specific efficacy in managing post-operative complications following impacted third molar surgery. Existing studies are often limited in scope and methodology, necessitating further investigation to fully understand their potential benefits. Therefore, this study aims to address these research gaps and provide definitive answers to the study main questions.

1.2.Statement of the Problem

Impacted third molar extraction is the most commonplace surgical procedure in oral surgery (Brković et al., 2017). This surgical procedure results in the most common detected post-operative complications which are trismus, swelling, and pain due to the inflammatory process (Bataineh & Batarseh, 2017). To treat post-operative complications, many strategies have been developed to decrease clinical occurrence after surgery through a pharmacological approach by inhibiting inflammatory processes of acute inflammation. Out of these, corticosteroids and NSAIDs have shown immunosuppressive, anti-inflammatory, and analgesic effects (Isola et al., 2016; Kaplan & Eroğlu, 2016). Though, the use of corticosteroids or NSAIDs has been related to some side

effects like gastrointestinal bleeding, renal function disturbance, a reduction in platelet function, shortness of breath, and profound hypotension (Piecuch, 2012).

Therefore, researchers have been working on alternative therapies including the use of therapeutic enzymes and phytotherapeutic drugs composed of herbal extracts. A proteolytic enzyme, serratiopeptidase, has shown positive results in inflammatory disorders around teeth and dental implants (Sanninol et al., 2013; Villafuerte-Nuñez et al., 2013). So far, published studies assessing the efficacy of serratiopeptidase after third molar extraction are minor with inadequate methodological quality (Al-Khateeb & Nusair, 2008; Chopra et al., 2009; Mouneshkumar et al., 2015).

In contrast, for many years, many phytotherapeutic drugs have been widely used for the treatment of inflammatory diseases and postsurgical conditions (Olmedo-Gaya et al., 2016; Pavan et al., 2012). There were favorable effects in the inflammatory parameters, when the phytotherapeutic drugs were used as a post-operative therapy of third molar surgery. The phytotherapeutic drug as a mixture of herbal extract with anti-inflammatory activity was shown to be safe and simple in the control of pain and control postsurgical discomfort after surgical removal of the third molar. Further studies are needed to understand better the role and potential benefits of phytotherapeutic drugs in the therapy after the removal impacted third molar (Isola et al., 2019). Escin is a natural molecule with a major active component of *Aesculus hippocastanum*. It is a natural mixture of triterpene saponins and has shown clinically considerable anti-inflammatory activity postoperatively and in traumatic injuries (Wang et al., 2009).

Based on the research gaps recommend by (Al-Khateeb & Nusair, 2008; Chopra et al., 2009; Mouneshkumar et al., 2015) to assess the efficacy of serratiopeptidase after third molar extraction and (Isola et al., 2019) to understand potential benefits of escin after the removal impacted third molar, the study aims at finding solid answers to the following main questions:

1. Does serratiopeptidase, when used in addition to conventional drugs, offer greater efficacy in reducing post-operative pain, trismus, and facial swelling compared to conventional drugs alone following impacted third molar surgery?
2. Does escin, when used in addition to conventional drugs, offer greater efficacy in reducing post-operative pain, trismus, and facial swelling compared to conventional drugs alone following impacted third molar surgery?
3. When both serratiopeptidase and escin are used in addition to conventional drugs following impacted third molar surgery, which one demonstrates superior efficacy in reducing post-operative pain, trismus, and facial swelling?

1.3. Justification of the study

There is a high prevalence rate of impacted lower third molars with many complications. To the best of the researcher's knowledge, no clinical study has been conducted aiming to compare the efficacy of serratiopeptidase and escin after impacted third molar surgery in order to minimize in the most common detected post-operative complications.

1.4. Objectives of the study

Based on the above introduction and study question, the objectives can be classified into general and specific as follows:

General objective

The overall purpose of this study is to compare the efficacy of serratiopeptidase and escin in the reduction of post-operative complications (i.e., pain, trismus, and facial

swelling) following impacted third molar surgery, when both used in addition to conventional drugs.

Specific objective

1. Evaluate the efficacy of serratiopeptidase, when used in addition to conventional drugs, in reducing post-operative pain, trismus, and facial swelling following impacted third molar surgery.
2. Evaluate the efficacy of escin, when used in addition to conventional drugs, in reducing post-operative pain, trismus, and facial swelling following impacted third molar surgery.

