1.5. Study Hypotheses

Based on the study main problem, objectives, and literature review, three main hypotheses are constructed in order to test the relationship between the study variables.

These hypotheses are listed in this section as follows:

1. There is a statistically significant difference in serratiopeptidase, when used in addition to conventional drugs, in reducing post-operative pain, trismus, and facial swelling compared to conventional drugs alone following impacted third molar surgery.
2. There is a statistically significant difference in escin, when used in addition to conventional drugs, in reducing post-operative pain, trismus, and facial swelling compared to conventional drugs alone following impacted third molar surgery.
3. There is a statistically significant difference in serratiopeptidase in reducing post-operative pain, trismus, and facial swelling compared to escin, when

both used in addition to conventional drugs, following impacted third molar surgery.

Chapter 2:

Literature Review

2.1.Impacted Third Molar

The third molars, commonly known as wisdom teeth, often lead to complications during eruption, presenting a frequent concern in oral surgery (Wray et al., 2003). (Lytle, 1979) defines an impacted tooth as “*a tooth that has failed to erupt into its normal functional position beyond the time usually expected for such appearance. Eruption may have been prevented by adjacent hard or soft tissue including tooth, bone, or dense soft tissue*”. Among impacted teeth, mandibular third molars are the most common, followed by maxillary third molars and maxillary canines. Most unerupted teeth are extracted due to pain or infection, but other reasons include involvement in pathologies like cysts or tumors, causing resorption of adjacent teeth, or interfering with surgical procedures (Undrell Moore, 2011).

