The split-mouth design compares treatments within each patient, avoiding bias that may arise when comparing separate cases and controls. It eliminates inter-subject variability and produces reliable results (Kazancioglu et al., 2014; Lesaffre et al., 2007). Compared to between-patient designs, the split-mouth design offers increased efficiency, requiring fewer participants and resources while achieving similar results. However, it also presents the potential for carry-across effects, where the treatment on one side of the mouth influences the response on the other side (Hujoel & Loesche, 1990; Varma & Chilton, 1974). To estimate treatment effects in a split-mouth design, researchers make assumptions about carry-over effects. Common assumptions include no carry-over effect, complete carry-over effect, and partial carry-over effect. These assumptions cannot be tested within the study itself and rely on prior knowledge (Hujoel & DeRouen, 1992).

When choosing a split-mouth design, researchers should consider bias, recruitment challenges, efficiency, and statistical analysis. Careful evaluation of potential carry-over effects is crucial to avoid bias. Finding suitable patients with symmetrical dental conditions can be difficult, and statistical analysis requires more complex methods compared to whole-mouth designs (Hujoel, 1998). Controlling carry-over effects in split-mouth studies is challenging. Washout periods of at least three weeks between treatment applications can help mitigate carry-over effects by allowing the body to eliminate residual effects of previous treatments (Gozali et al., 2017). Understanding the advantages, limitations, statistical considerations, and implications of the split-mouth design is essential for researchers in both the statistical and clinical fields. This knowledge

enables effective utilization of the design while acknowledging its potential drawbacks (Lesaffre et al., 2009).

Chapter 3:

Material and Methods

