3.1. Study Design

This clinical trial will utilize a split-mouth design, randomly assigning two different treatments to each half of the patient's mouth. From this randomized study which is characterized by a triple-blind study, the procedures are going to be performed by qualified and experienced professional. However, the operator will have no access to data evaluated. The evaluator will have access to all responses of the symptoms of patients and will not know the treatment that is going to be selected, while the patient is unaware of which treatment or intervention is being applied to each side of their mouth. This stringent blinding approach minimizes potential biases and significantly enhances the scientific validity of the study.

Patients will be assigned into two groups and each patient acted as their own control using the split-mouth technique. One impacted third molar will be removed from one side and will receive conventional drugs while the other side will be removed after 3 weeks (wash-out period) and receive additional treatment beside the conventional drugs (i.e., either enzyme or herbal). The two groups will be classified as follows:

- The first group will receive conventional drugs with 10mg oral serratiopeptidase at immediate post-operative time and three times a day for post-operative five days on the first surgical visit and on the second surgical visit (after 3 weeks) conventional drugs will be given only or vice versa.
- The second group will receive conventional drugs with 20mg oral escin at immediate post-operative time and three times a day for post-operative five days on the first surgical visit and on the second surgical visit (after 3 weeks) conventional drugs will be given only or vice versa.

The conventional drugs, it will be administered to patients in the two groups, includes: Amoxicillin 500mg Cap b.i.d., Metronidazole 500mg Tab t.i.d., Diclofenac sodium 50mg Tab b.i.d.

3.2.Study Population

The study population will include patients who will visit the dental clinics in the College of Dentistry, University of Science and Technology, Yemen (USTY) for impacted mandibular third molars extraction during 2024.

3.3.Sample Size

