The sample size is the number of participants planned to be included in the trial, usually determined using a statistical power calculation (Zanatta et al., 2017). This study determined the sample size using a power calculation based on previous research by (Costa et al., 2015). Their study found that preemptive use of etoricoxib 120mg significantly reduced the need for rescue analgesic medication compared to a placebo (1.6 ± 1.3 vs 4.0 ± 2.5). To achieve a power of 80% and a confidence interval of 95%. The study will need to evaluate 11 surgical sites per sub-group (<http://www.openepi.com/SampleSize/SSMean.htm>). To account for a potential 20% drop-out rate, a total of 14 sites per sub-group will be recruited. This will result in a total sample size of 56 dental units (2 teeth per patient) from 28 patients. The following Table 3-1 illustrates the study sample size and the planned treatment.

Table 3-1 : Sample Size and Study Treatment.

Groups	I		II		Total
Patients	14		14		28
Sub-groups	Control 1	Study 1	Control 2	Study 2	4
Sample size	14	14	14	14	56
Conventional Treatment	Amoxicillin 500mg Cap b.i.d		Metronidazole 500mg Tab t.i.d		N/A
	Diclofenac sodium 50mg Tab b.i.d				
Study Treatment	N/A	Serratiopeptidase 10mg t.id	N/A	Escin 20mg t.id	N/A

3.4.Sample Selection

Patients who will undergo to surgical removal of the impacted third molar will be assessed for their eligibility to participate according to the following inclusion and exclusion criteria:

Inclusion criteria:

- Medically fit patients.
- The presence of two asymptomatic mandibular third molar indicated for surgical extraction.
- Absence of pericoronitis or signs of inflammation during the last 30 days

Exclusion criteria:

- Patient administered other drugs such as NSAIDS and steroids.
- Patient has allergy to the drugs used in this study.
- Pregnant patient or a patient with lactation.
- Immunocompromised patients with diabetic or hypertension (from patient's history).
- Patients with irradiated maxillofacial region.
- Intellectually disabled patients and patients unable to come for follow up visits.
- Patients with acute and subacute pericoronitis

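### Serratiopeptidase versus escin, the stated overall purpose, is the least precise of the three planned contrasts, and the paired tests in section 3.9 cannot test it

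*Combined protocol and SAP*

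**What the plan says.** The general objective in section 1.4 reads: "The overall purpose of this study is to compare the efficacy of serratiopeptidase and escin". Hypothesis 3 in section 1.5 repeats the target: "There is a statistically significant difference in serratiopeptidase in reducing post-operative pain, trismus, and facial swelling compared to escin". The two specific objectives concern each drug against conventional drugs alone; the first is "Evaluate the efficacy of serratiopeptidase, when used in addition to conventional drugs, in reducing post-operative pain, trismus, and facial swelling following impacted third molar surgery", and the second says the same of escin.

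Section 2.3 favours the split-mouth design on these grounds: "The split-mouth design compares treatments within each patient, avoiding bias that may arise when comparing separate cases and controls". Section 3.1 then gives each group one drug in one session, while "on the second surgical visit (after 3 weeks) conventional drugs will be given only or vice versa". Section 3.3 adds: "This will result in a total sample size of 56 dental units (2 teeth per patient) from 28 patients". Table 3-1 splits them into 14 patients with serratiopeptidase (S) and control (C), and 14 with escin (E) and control. No patient receives both S and E.

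Section 3.9 names the paired t test or the Wilcoxon test, after a Shapiro–Wilk check, and no other comparison. Section 3.3 gives no power or precision for S against E.

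**The concern.** Half of the 56 sessions are control and none of the pairs is S with E. The contrast that carries the general objective is therefore the only one of the three never made directly within a patient. It has to be assembled from two sets of patients, which adds their sampling errors together.

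Two things are at stake. First, hypothesis 3 has no usable test, because a paired test needs both treatments in the same patient. Second, even with a suitable analysis, a difference between the drugs that matches what the trial can detect for drug against control would be found only about half the time. An inconclusive result could then be misread as the two drugs performing alike.

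**Working it through.** **The plan's own figure.** Inputs from section 3.3: means 1.6 and 4.0, SDs 1.3 and 2.5, power 80%, confidence 95% (two-sided 5% assumed).

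n per sub-group = (1.3² + 2.5²) × (1.960 + 0.842)² / (4.0 − 1.6)² = 7.94 × 7.85 / 5.76 = 10.8, so 11. With 20% drop-out, 11 / 0.8 = 13.75, so 14. Both figures reproduce. They come from a comparison of two independent means, active against placebo, and do not address S against E.

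**Notation and assumptions.** Let sd_d² = 2σ²(1 − ρ) be the variance of one within-patient difference, where ρ is the within-patient correlation. The documents give no ρ, so a range is shown. Assumed throughout: equal variances, an additive session effect with order balanced within each pairing, and no carry-over.

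**Difference-only analysis, planned 14/14.**
- Var(S−C) = Var(E−C) = sd_d²/14.
- Var(S−E) = sd_d²(1/14 + 1/14) = sd_d²/7, which is twice as large.

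**Mixed model, planned 14/14 (patient as a random effect).**
- Var(S−E) = 2σ²(1 − ρ²)/14.
- Var(S−C) = σ²(1 − ρ)(3 + ρ)/28.
- Ratio = 4(1 + ρ)/(3 + ρ).

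The ratio is 1.33, 1.58, 1.71 and 1.84 at ρ = 0, 0.3, 0.5 and 0.7. A better analysis narrows the gap but does not close it.

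**Example re-pairing, 10 S/C, 10 E/C, 8 S/E.** Information is direct plus indirect, in units of 1/sd_d²:
- S−C (and E−C): 10 + (10 × 8)/(10 + 8) = 14.4, against 14 planned; variance about 3% lower.
- S−E: 8 + (10 × 10)/(10 + 10) = 13, against 7 planned; ratio 13/7 = 1.86, a cut of 1 − 7/13 = 46%.

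Under the mixed model (σ² = 1):

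| ρ | S−E planned | S−E re-paired | Ratio | Cut |
|---|---|---|---|---|
| 0 | 0.143 | 0.111 | 1.29 | 22% |
| 0.3 | 0.130 | 0.089 | 1.46 | 31% |
| 0.5 | 0.107 | 0.068 | 1.57 | 36% |
| 0.7 | 0.073 | 0.043 | 1.69 | 41% |

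The S−C and E−C variances change by between −1.5% and +0.6%.

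**Power** (noncentral t, two-sided 5%, noncentrality = difference/sd_d × √information). The reference difference is 0.81 sd_d, which 14 pairs detect with 80% power on 13 degrees of freedom. The joint model has 25 degrees of freedom with 28 patients and 19 with 22.

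| Contrast and analysis | Planned | Re-paired |
|---|---|---|
| S−E, 28 complete | 54% | 80% |
| S−E, 22 complete (11/11 or 8/8/6; information 5.5 or 10) | 44% | 68% |
| S−E at half the difference, 28 complete | 18% | 29% |
| S−C or E−C, joint model | 83% | 84% |
| S−C or E−C, paired t test on direct pairs only | 80% (14 pairs) | 63% (10 pairs) |

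**The case against.** The control sessions have a purpose. Section 1.5 lists three main hypotheses, and two of them, with both specific objectives, need drug against conventional drugs alone. The sample size was also built on an active-against-placebo comparison. S against E remains estimable from the two groups, so the allocation is an efficiency trade-off and not a contradiction. All of that stands. It is why the re-pairing is put as an option and why it keeps control in 20 of the 28 patients.

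Several stronger readings are tempting, and the documents do not support them.
- A reader might infer that S against E has no within-patient control as planned. It has: each patient's own level drops out of both differences. What is lost is precision.
- A reader might infer a flat factor of two against what the same 28 patients could give. The factor depends on benchmark and analysis. It is 1.86 for 10/10/8 in a difference-only analysis and 1.29 to 1.69 under the mixed model. It is 2.0 for an even three-way split with differences only, and 4 if all 28 received both drugs, which would abandon the two specific objectives.
- A reader might infer that S/E pairs remove a bias from setting an extra product against none. If that effect is equal for both drugs, it already cancels in the planned contrast. In the example, 5 of the 13 units of information still pass through control.
- A reader might infer that re-pairing costs the other two contrasts nothing. That holds only with the joint model. With paired t tests on the direct pairs alone, power falls from 80% to 63%, and a simple Wilcoxon test cannot use the indirect evidence.

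**Conclusion.** The point holds as a weakness in precision and a gap in the analysis, not as an invalid design. The contrast named as the overall purpose has twice the variance of the other two in a difference-only analysis, and 1.33 to 1.84 times under a mixed model for ρ from 0 to 0.7. Section 3.9 offers no test for it.

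The missing analysis is the firmer part, since it follows from the text alone. The gain from re-pairing rests on the assumptions listed in the working, and on the two drugs differing by as much as the drug-versus-control effect that 14 pairs can detect. At half that difference, neither allocation has useful power. The mixed-model figures also need random allocation to group; the draws listed in section 3.5 cover tooth, intervention and session, but not group.

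**What to change.** 1. **Section 3.9, whatever the allocation.** Replace the separate paired tests with one model containing patient, session and treatment, and report S−C, E−C and S−E with confidence intervals. State in advance whether patient is fixed (difference-only) or random (mixed model). This costs only a rewrite of the section. On the planned allocation it also lifts power for S−C and E−C at 0.81 sd_d from 80% to 83%.

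2. **Before allocation starts, consider three pairings.** For example, allocate the same 28 patients as 10 S/C, 10 E/C and 8 S/E, with order balanced 5/5, 5/5 and 4/4 and the regimens as written. Amend section 3.1, section 3.3, Table 3-1 and section 3.5. Section 3.5 would need blocked rather than simple randomization, with pairing and order both drawn.

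The second change needs no extra patients, visits or surgeries, but it has downsides to weigh:
- Direct drug/control pairs fall from 14 to 10 per drug, and hypotheses 1 and 2 then depend on the joint model.
- The simple Wilcoxon fallback no longer uses all the evidence, so another fallback must be named.
- Eight patients receive both products, in separate sessions, and eligibility must cover both products for every patient.
- The no-carry-over assumption, which section 2.3 says cannot be tested within the study, extends to one product followed by the other.

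If the sponsor keeps 14/14, section 3.3 should state the precision expected for S against E and acknowledge that it is the weakest of the three contrasts.
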